8.3. Multiplicity and Experiment-wise Alpha Control Considerations

This is a Phase 2 dose-finding study, powered only for the primary efficacy endpoint; outcomes from this study are expected to be used to determine the dose to carry forward into Phase 3. Secondary efficacy

This document is confidential.

endpoints are expected to contribute data providing evidence of benefit from BPN14770 treatment and to be used as part of the preponderance of evidence in the dose-selection decision-making. Due to the limited sample size in this Phase 2 dose-finding study, experiment-wise alpha control will be limited to control for the two pairwise tests for the primary efficacy endpoint only.

- BPN14770 25 mg vs placebo
- BPN14770 10 mg vs placebo

A hierarchical approach will be taken, in which the 25 mg vs placebo comparison will be tested first, and only if statistically significant ($p\text{-value} \leq 0.05$) will testing of the 10 mg vs placebo comparison be performed. This will ensure alpha control of the primary endpoint for the study as well as a gated procedure for the secondary endpoints for each dose. Only if the primary efficacy endpoint for a given dose is found to be statistically significant will the other efficacy endpoints will be tested at their nominal p -values, with no control for multiple testing.

This document is confidential.

9. Analysis Of Pharmacokinetics

Plasma BPN14770 concentrations will be obtained during the Week 1, 4, 8 and 13 clinic visits. Samples will be drawn according to the time of the clinic visit, with documentation of time of day sampling was performed, and time of day of most recent dose of study medication.

Plasma BPN14770 concentrations will be descriptively summarized by dose and visit for the PK Population. Concentration values below the lower limit of quantification (BLQ) will be treated as zero.

A listing for Plasma BPN14770 concentrations with dose, visit, and collection time will be produced.

This document is confidential.

10. Analysis Of Biomarker Data

Biomarker data will be analyzed post-study in an exploratory fashion. This SAP does not address those analyses.

This document is confidential.

11. Safety

The population used for safety analyses will be the Safety Population. Safety will be assessed on the basis of treatment-emergent adverse events (TEAEs), clinical laboratory values, vital signs, physical exams, the Columbia-Suicide Severity Rating Scale (C-SSRS), and ECGs.

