Study Title:	A Randomized, Double-blind, Placebo-controlled, 3-Arm Parallel Design Study to Evaluate the Effects of BPN14770 in Patients with Early Stage Alzheimer's Disease
Study Number:	BPN14770-CNS-201
Study Phase:	Phase 2

Subjects will have a total of eight clinic visits: Screening; Baseline (Day 1); Weeks 1, 2, 4, 8, 13, and the final Follow-up Visit. Cognitive testing will be performed during each clinic visit except the final Follow-up Visit. Safety and tolerability assessments throughout the study will include adverse event monitoring, ECGs, vital signs, blood chemistry, hematology; urinalysis will be performed at Screening, Baseline, and Weeks 1, 4, and 13, and lipid evaluations at Baseline and Week 13. Should gastrointestinal (GI) side effects occur, nausea may be treated with 5-HT3 antagonists, and diarrhea may be treated with loperamide. Anticholinergic drugs may not be used to treat GI side effects.
 
Pharmacokinetic samples will be collected during the treatment period to confirm that study drug is present, and to estimate plasma exposure at Weeks 1, 4, 8 and 13.
 
An independent data and safety monitoring board (DSMB) will provide safety oversight for this study. The DSMB will consist of two qualified MDs and one statistician. The DSMB will review standard safety data approximately every four (4) months, based on enrollment rate. A DSMB charter will be developed to further outline the DSMB responsibilities and the desired listings, summaries and analyses.
	

Planned Numbers of Subjects: A target of 80 evaluable subjects per group (240 total) is planned. Approximately 85 subjects per group will be enrolled (255 total) in order to account for potential dropouts.
	

Name of Sponsor/Company:	Tetra Discovery Partners, Inc.
Name of Investigational Product:	BPN14770
Study Title:	A Randomized, Double-blind, Placebo-controlled, 3-Arm Parallel Design Study to Evaluate the Effects of BPN14770 in Patients with Early Stage Alzheimer's Disease
Study Number:	BPN14770-CNS-201
Study Phase:	Phase 2

Study Procedures:

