Pharmacokinetic analyses found that steady-state appeared to be reached after 3 to 4 days of BID or QD dosing in both young and elderly subjects. After a single oral dose of BPN14770 in healthy young subjects, C_{max} and AUC_{12} appeared to increase in a dose-proportional fashion over the dose range of 15 to 50 mg, with a greater than proportional increase in exposure observed after a 75-mg dose. Following BID dosing of BPN14770 in healthy young subjects, C_{max} and AUC_{12} appeared to increase in a greater than dose-proportional fashion from 15 mg to either 30 mg or 50 mg. A moderate degree of accumulation (up to approximately 5-fold) was observed after BID dosing in healthy young subjects, with less accumulation (approximately 2-fold) after QD dosing.

After a single oral dose of BPN14770 in healthy elderly subjects, C_{max} appeared to increase in a greater than dose-proportional fashion over the dose range of 10 to 40 mg, whereas AUC_{12} appeared to increase in a greater than dose-proportional fashion from 10 mg or 20 mg to 40 mg. Following BID dosing of BPN14770 in healthy elderly subjects, C_{max} and AUC_{12} appeared to increase in a greater than dose-proportional fashion over the dose range of 10 to 40 mg. A moderate degree of accumulation (up to approximately 4-fold) was observed after BID dosing in healthy elderly subjects.

In healthy young subjects, mean peak to trough fluctuation was similar among BID regimens, ranging from 171% to 179%, and was 337% for the QD regimen. In healthy elderly subjects, mean peak to trough fluctuation was similar among BID regimens, ranging from 156% to 249%.

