4.4.4 Pharmacokinetic Endpoints

Plasma BPN14770 concentrations at Weeks 1, 4, 8, and 13, to verify that study drug is present and to estimate plasma exposure at these time points.

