5.2 Dose Selection

Doses of 10 and 25 mg BPN14770 to be taken twice daily were chosen for testing in this study.

Based on pharmacokinetic data from study BPN14770-CNS-102 (MAD), steady state average plasma concentrations of BPN14770 10 mg are projected to be approximately 60 ng/ml. Therefore, the lower dose of 10 mg has the potential to demonstrate efficacy in this study, although given the uncertainties of translation from preclinical models, it may be below the effective range. On the other hand, the 25 mg dose should be above that needed for efficacy, and is estimated to produce steady state with projected average plasma levels of concentrations over 200 ng/ml. The twice-daily doses of 10 mg and 25mg selected for this study both fall well within the tolerance limits defined by the SAD and MAD studies.

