8.8 Laboratory Assessments

Appendix 16.2 [Clinical Laboratory Analytes](#) provides a list of the clinical laboratory tests that will be performed according to the collection schedule provided in the [Schedule of Assessments](#).

Blood samples for chemistry, hematology and lipid testing and urine samples will be collected in accordance with acceptable laboratory procedures. Blood samples for chemistry, hematology and lipid testing performed on Day 1 and Week 13 require an 8 hour fast and will include glucose testing; samples obtained at all other visits do not require fasting and will not include glucose or lipid testing.

A central laboratory will be used to analyze the clinical laboratory samples.

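### The PK table by dose and visit ignores the recorded time since last dose, so it shows drug presence but does not give an interpretable level or week-to-week change of exposure

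*SAP*

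**What the plan says.** Protocol Section 4.4.4 gives the Week 1, 4, 8 and 13 concentrations two purposes: "to verify that study drug is present and to estimate plasma exposure at these time points". The protocol Synopsis repeats both: "to confirm that study drug is present, and to estimate plasma exposure at Weeks 1, 4, 8 and 13".

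Sampling is not timed to the dose. SAP Section 9 says: "Samples will be drawn according to the time of the clinic visit, with documentation of time of day sampling was performed", and it also records the "time of day of most recent dose of study medication". Protocol Section 8.14.1 agrees.

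The planned analysis is one sentence in SAP Section 9: "Plasma BPN14770 concentrations will be descriptively summarized by dose and visit for the PK Population". Under SAP Section 6.1 that means n, mean, SD, median, minimum and maximum. Values below the quantification limit are set to zero. The Section 9 listing names dose, visit and collection time, but not the time of the last dose. Protocol Sections 8.14.4 and 11.6 plan the same kind of table, so the SAP follows the protocol here. Neither document derives time since dose, defines an exposure parameter or plans a PK model.

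On variation within the dosing interval, protocol Section 4.3.2.2 reports for healthy elderly subjects that "mean peak to trough fluctuation was similar among BID regimens, ranging from 156% to 249" percent.

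**The concern.** A single concentration depends on dose, on the subject's clearance and on the time since the last capsule. If the third is ignored, a visit mean mixes samples near the peak with samples near the trough in unknown proportions. A rise or fall between Week 1 and Week 13 could then reflect a change in clinic hours and not a change in exposure.

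Two stated uses are affected. One is estimating exposure at each time point. The other is the intention, in protocol Section 4.2, to correlate PK with cognitive and safety outcomes. Neither document specifies that correlation, and individual concentrations would need time since dose to be read that way. The times needed to resolve this are already collected.

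**Working it through.** **Inputs.** Dosing interval about 12 h (protocol Section 7.6). Tmax 1.5 to 3 h and terminal half-life 11 to 13 h (Section 4.3.2.1, single dose). Mean peak-to-trough fluctuation 156-249% in healthy elderly subjects on 10, 20 and 40 mg twice daily (Section 4.3.2.2). The documents give no clock times for visits, so the sampling windows below are assumptions.

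**The plan's own figure.** The 156-249% is an observed result. The documents give no formula for it and no Cmax, Cmin or Cavg, so it cannot be reproduced. As a plausibility check, take the one-compartment oral profile at steady state with τ = 12 h:

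C(t) ∝ ka/(ka − ke) × [e^(−ke·t)/(1 − e^(−ke·τ)) − e^(−ka·t)/(1 − e^(−ka·τ))]

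Here ke = ln 2 / half-life, and ka is chosen so that ln(ka/ke)/(ka − ke) equals Tmax. The documented half-life and Tmax give 45-63% as (Cmax−Cmin)/Cavg, 60-92% as (Cmax−Cmin)/Cmin, or a Cmax/Cmin ratio of 1.60-1.92. The reported fluctuation exceeds the first two. The third falls inside 1.56-2.49. Three readings are therefore carried forward.

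**Size.** For each reading, ke was fitted so that fluctuation equals 1.56 or 2.49, with Tmax 1.5 or 3 h. The mean of C(t) over the window was then divided by the 12-hour average. The last row uses the documented half-life and Tmax with no fitting.

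| Basis | Samples at 1-4 h | Samples at 8-12 h | Uniform over 0-12 h |
|---|---|---|---|
| (Cmax−Cmin)/Cmin | 1.34-1.47 | 0.60-0.69 | 1.00 |
| Cmax/Cmin | 1.16-1.34 | 0.70-0.85 | 1.00 |
| (Cmax−Cmin)/Cavg, Tmax 1.5 h only (no fit at 3 h) | 1.67-2.16 | 0.19-0.47 | 1.00 |
| Documented half-life and Tmax | 1.18-1.24 | 0.78-0.84 | 1.00 |

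**Apparent change between visits.** Take the mildest fitted case, with samples clustering early at one visit and late at another. The ratio of visit means is 1.16/0.85 = 1.36 with no change in exposure. For the 10 mg arm, "steady state average plasma concentrations of BPN14770 10 mg are projected to be approximately 60 ng/ml". The two visit means would then read 60 × 1.16 = 70 and 60 × 0.85 = 51 ng/mL. A complete shift from one window to the other is the limiting case, so a partial shift gives less.

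**Noise when timing is uniform.** Under (Cmax−Cmin)/Cmin, timing alone gives a between-sample CV of 27-37%. For a mean of 80 subjects that contributes 0.27/√80 = 3.0% to 0.37/√80 = 4.1% of the mean. The issue is systematic clustering, not random scatter.

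**The case against.** The case on the other side is substantial. The endpoint is worded as plasma concentrations at four visits, the objective is only to obtain PK data, and no AUC or average concentration is promised. Drug presence is shown by the planned table. The summary is split by dose as well as visit and reports spread as well as mean. If sampling times were spread evenly over the interval, the group mean would sit close to the true average. All of this stands. It means the table is limited, not useless. The purpose of estimating exposure remains, and the plan neither arranges nor checks an even spread.

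The model is also only indicative. It does not reconcile all the PK figures. With the documented half-life it predicts about 1.9- to 2.1-fold accumulation, against the 3- to 5-fold after twice-daily dosing in protocol Section 4.2. Higher accumulation would point to a flatter profile and a smaller effect. The direction of the problem does not depend on the model, but its size does.

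Four stronger readings are tempting and not supported:

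- **That the dose contrast is distorted.** The arms are randomised, blinded and on one visit schedule, so sampling times should be distributed alike. With similarly shaped profiles the contrast stays fair. Setting an individual's swing within an interval against the projected gap between dose averages compares unlike quantities.
- **That Week 13 differs because it is a fasting visit.** Safety blood samples "performed on Day 1 and Week 13 require an 8 hour fast", but nothing says the dose is withheld or the clinic hour changes.
- **That PK supports the Phase 3 dose choice.** SAP Section 3.1 refers to study outcomes in general, and Section 8.3 names efficacy endpoints. Neither mentions PK in that role.
- **That last-dose time will not be reported at all.** Section 6.1 says all subject data will be listed. The gap is that the Section 9 listing does not name it and no analysis uses it.

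**Conclusion.** The point holds in a limited form. The table in SAP Section 9 meets the first PK purpose, drug presence. It does not give an interpretable absolute level of exposure or an interpretable change from week to week, because both depend on uncontrolled sampling times that the plan records but does not use.

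Across the two readings (Cmax−Cmin)/Cmin and Cmax/Cmin, the visit mean lies between 0.60 and 1.47 times the true average when samples cluster late or early, and near 1.0 when they are uniform. This rests on assumed windows, a one-compartment model, an undefined fluctuation formula, and means from healthy elderly subjects in an earlier study.

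A reader might infer that exposure cannot be estimated at all. That goes too far, since evenly spread samples would give a group mean near the average. The matter is a cheap improvement to a descriptive objective. It does not touch the primary analysis, and it is a weakness shared with the protocol, not a departure from it.

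**What to change.** In SAP Section 9:

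- Derive time since last dose for every sample, and add it and the last-dose time to the concentration listing.
- Plot concentration against time since dose, by dose level.
- Summarise by dose, visit and pre-specified time-since-dose window. Place the boundaries so that absorption and peak are separate from later times; a single 0-4 h window would mix drug first appearing at 0.5-1 h with the 1.5-3 h peak.
- Add a category above 14 h for late samples. Protocol Section 10.10 takes a PK sample at early termination, and the visit reassignment in SAP Section 6.4 covers efficacy only, so it is open where such samples are counted. With values below quantification set to zero, a late sample could pull a visit mean down.
- Keep the by-visit table, labelled as evidence of drug presence only.

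The cost is one table, one plot and two listing columns from data already collected. The drawback is fewer subjects per cell, so some windows may support only the plot. Binned values still do not give individual exposure, which would need a population PK model if the correlation in protocol Section 4.2 is to be pursued.

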11.1. Extent of Exposure

The following information will be summarized using descriptive statistics by the treatment group:

- Duration of exposure (days)
- Total number of capsules taken
- Cumulative dose (mg)

Duration of exposure will be calculated as:

$$\text{Date of last dose} - \text{date of first dose} + 1.$$

Total number of capsules taken will be calculated as:

Sum of (Number of capsules dispensed at previous visit - Number of capsules returned) over all the visits.

Cumulative dose will be calculated as:

$$\text{Total number of capsules taken} \times \text{dose level}$$

The listing for the exposure data will be provided.

11.2. Treatment Compliance

Treatment compliance will be calculated for each visit and overall for the treatment period.

Compliance (%) for each visit will be calculated as:

$$(\text{Number of capsules actually taken} / \text{Number of capsules planned}) * 100\%$$

Number of capsules actually taken = Number of capsules dispensed at previous visit - Number of capsules returned/remained.

Number of capsules planned = (current visit date – previous visit date)*2 – 1 (if last dose is in AM) + 1 (if last dose at previous visit is in AM). If last dose information is missing, last dose will be treated as AM dose.

Compliance (%) for overall will be calculated as:

$$(\text{Total number of capsules taken} / \text{Total number of capsules planned}) * 100\%$$

This document is confidential.

Total number of capsules taken is calculated as in [Section 11.1](#); Total number of capsules planned is calculated as (Date of last dose – date of first dose) * 2.

Compliance to study medication will be summarized using descriptive statistics for each visit and overall by treatment group.

Compliance will also be listed along with the study medication accountability data.

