10.4 Week 1 (Day 7 ± 2)

The following assessments will be completed at the Week 1 visit:

- Collect vital signs;
- Conduct ECG (single);
- Draw blood samples for Chemistry and Hematology (fasting or nonfasting);
- Draw blood samples for pharmacokinetic analysis and biomarkers;
- Collect urine for safety urinalysis;
- Conduct C-SSRS assessment;
- Conduct RBANS, MMSE, and CGI-I evaluations;
- Record pill count remaining in bottle to assess dosing compliance;

- Record any updates to concomitant medication use; and
- Assess and record and adverse events.

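### The SAP 11.2 capsule formula gives a negative Week 2 compliance for a fully compliant subject, because no drug is dispensed at Week 1

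*SAP*

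**What the plan says.** SAP 11.2 (Treatment Compliance) reports compliance for each visit and overall. The per-visit numerator is "Number of capsules actually taken = Number of capsules dispensed at previous visit - Number of capsules returned/remained". The denominator is twice the days since the previous visit, less 1 if the current last dose was a morning dose, plus 1 if the last dose at the previous visit was a morning dose. It adds: "If last dose information is missing, last dose will be treated as AM dose".

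For the whole treatment period, SAP 11.2 takes the numerator from SAP 11.1, where it is "Sum of (Number of capsules dispensed at previous visit - Number of capsules returned) over all the visits". SAP 11.1 also multiplies that total by the dose level to give cumulative dose. The overall denominator is stated as "Total number of capsules planned is calculated as (Date of last dose – date of first dose) * 2".

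The schedule of assessments (Protocol 16.1; SAP Table 2) marks medication accountability at Weeks 1, 2, 4, 8 and 13, but dispensing only at Baseline and Weeks 2, 4 and 8. The only drug-related step listed in Protocol 10.4 for Week 1 is "Record pill count remaining in bottle to assess dosing compliance". Protocol 10.5 has the site collect, count and dispense at Week 2.

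**The concern.** The numerator assumes that every accountability visit follows a visit at which drug was handed out. Week 2 does not. Its previous visit is Week 1, where nothing was dispensed and the Baseline supply went home again with the subject. The dispensed term is therefore 0, the remaining term is positive, and the difference is negative. Neither section carries the capsules kept at Week 1 forward.

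The two sections also describe the subtracted quantity differently. SAP 11.2 covers capsules returned or remaining; SAP 11.1 covers capsules returned only. If a programmer uses one count variable for both, the Week 1 remainder is subtracted in SAP 11.1 although those capsules are taken later.

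At stake are the by-visit compliance table, the compliance listing and, under the second reading, the exposure table and overall compliance.

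**Working it through.** **Inputs**
- First dose: evening of Day 1 (Protocol 7.6), then two capsules a day.
- Target days: 7, 14, 28, 56 and 91, with windows of 2 days at Weeks 1 and 2 (Protocol 10.4 to 10.8).
- Supply per subject: six 34-count bottles and one 12-count bottle (Protocol 7.2), so 6 × 34 + 12 = 216 capsules.
- Assumption: the last dose before each visit is the morning dose of that day.

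**Reproducing the stated supply.** The need in each dispensing interval is 2 × days: 26 (Day 1 to 14), 28, 56 and 70. The fewest bottles that cover these are 34, 34, 2 × 34 and 2 × 34 + 12. That makes six 34-count bottles and one 12-count bottle, 34 + 34 + 68 + 80 = 216, exactly as stated. The documents do not give the split by visit. A single 34-count bottle at Baseline is an inference, supported by this match and by Protocol 7.5, which refers to the subject's bottle in the singular.

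**SAP 11.2 applied literally to a subject who misses no dose**

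| Visit | Dispensed at previous visit | Remaining | Formula: taken | Planned | Compliance | Actually taken |
|---|---|---|---|---|---|---|
| Week 1 | 34 | 22 | 12 | 6 × 2 - 1 + 1 = 12 | 100% | 12 |
| Week 2 | 0 | 8 | -8 | 7 × 2 - 1 + 1 = 14 | -57.1% | 14 |
| Week 4 | 34 | 6 | 28 | 28 | 100% | 28 |
| Week 8 | 68 | 12 | 56 | 56 | 100% | 56 |
| Week 13 | 80 | 10 | 70 | 70 | 100% | 70 |

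The Week 1 denominator of 12 relies on the missing-dose rule, which treats Baseline as if its last dose were a morning dose.

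**Visit windows at Week 2**
- Week 1 on Day 9 and Week 2 on Day 12: 22 taken, 12 left, planned 2 × 3 = 6, so -12/6 = -200%.
- Week 1 on Day 5 and Week 2 on Day 16: 30 taken, 4 left, planned 2 × 11 = 22, so -4/22 = -18%.
- Every other combination lies between these, so the value is always negative. A larger Baseline supply would make it more negative.

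**SAP 11.1 total under the two readings of returned**
- Physically collected only (nothing returned at Week 1): 34 - 8 + 28 + 56 + 70 = 180, which is correct. Overall compliance is 180/180 = 100%.
- Week 1 remainder entered as returned: 12 - 8 + 28 + 56 + 70 = 158. The shortfall is 22 capsules, 22/180 = 12.2%. Overall compliance is 158/180 = 87.8%. Cumulative dose is 1,580 instead of 1,800 mg in the 10 mg arm, and 3,950 instead of 4,500 mg in the 25 mg arm. The shortfall equals the Week 1 remainder, so across the Week 1 window it runs from 18/180 = 10.0% to 26/180 = 14.4%.

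**The case against.** The best defence is that a sensible programmer would read the previous visit as the previous dispensing visit. Used in both numerator and denominator, that gives (34 - 8)/26 = 100% at Week 2. The SAP does not say so, and the result would be compliance since Baseline, not since Week 1. Used in the numerator only, it gives 26/14 = 186%. Treating Week 1 as nothing returned does not help either: Week 2 stays at -57% and Week 1 becomes 34/12 = 283%. A negative value would probably be noticed in the output review described in SAP 15. That lowers the chance of publication but does not supply the missing rule.

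Four further inferences are tempting, and the documents do not support them as established:

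- **Exposure is understated by 12%.** Read as written, SAP 11.1 subtracts only returned capsules, and nothing is collected at Week 1. The total is then correct. The 12% needs the Week 1 count to be entered as returned.
- **The morning/evening terms have the wrong sign.** If the last dose means a dose on the visit date, the formula is right in all four combinations: 2d, 2d, 2d + 1 and 2d - 1, where d is the number of days between visits. It fails only if an evening dose means the night before and the pattern changes between visits. With a morning dose at the previous visit and the evening before at the current one, the true count is 2d - 1 against 2d + 1. That is 13/15 = 87% over 7 days, but 55/57 = 96% over 28 days. This is an undefined term, not a demonstrated error.
- **Subjects would be wrongly removed from the per-protocol or completers populations.** SAP 5.8 names substantial departures from the dosing schedule as possible major violations. However, deviations are collected by site monitors and reviewed by the project team, and no compliance percentage or cut-off is given. SAP 11.2 uses compliance only in summaries and listings.
- **The overall planned count is materially wrong.** It is one short when the last dose is in the evening: 180 against 181, about 0.6%.

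**Conclusion.** The Week 2 defect stands: the stated numerator contradicts the trial's own dispensing schedule and gives a negative compliance for any fully compliant subject with capsules left. The size is -57% under the inferred 34-count Baseline bottle, target-day visits and morning last doses, and -200% to -18% across the visit windows. The error in total capsules, cumulative dose and overall compliance is conditional: none if returned means physically collected, about 12% if the Week 1 count is used. The rule is the same in all arms, is confined to exposure and compliance reporting, and does not enter the primary analysis.

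**What to change.** 1. In SAP 11.2, define capsules taken at a visit as capsules on hand after the previous visit (kept plus newly dispensed) minus capsules remaining or returned now. Week 2 then gives 22 - 8 = 14, and 14/14 = 100%. The visits sum to 12 + 14 + 28 + 56 + 70 = 180.
2. In SAP 11.1, state that the sum uses only capsules physically returned at collection visits: Weeks 2, 4, 8 and 13, or early termination.
3. Keep the per-visit planned formula, including its treatment of Baseline as a morning last dose. Dosing starts on the evening of Day 1, so a rule that credits Baseline with no morning dose can go wrong: adding 1 for a morning dose on the current visit day and subtracting 1 for one on the previous visit day would give 13 at Week 1 instead of the correct 12.
4. State that a morning or evening last dose refers to a dose on the visit date, and that a last dose on the evening before is counted from its actual date.
5. Optionally, add 1 to the overall planned count when the last dose is in the evening.

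The cost is SAP wording and programming. No data collection changes, because the Week 1 count is already recorded.
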